8.5 Patient and Public Involvement

The HORIZONS Coordinating Centre research team has a long history of working closely with people living with and beyond cancer to design, develop and deliver research programmes and projects – our PPI Research Partners. We have worked with PPI Research Partners as Co-researchers, for example in the Macmillan Listening Study [1], and work alongside PPI Research Partners in our URGs and Knowledge Café events where we discuss, involve PPI Research Partners and engage the wider public in research ideas and on-going projects.

Involvement of PPI Research Partners and engagement with the wider public will benefit the HORIZONS Programme by enhancing the awareness, relevance and accessibility of the research. This will be achieved by working closely with PPI Research Partners in the HORIZONS URG to develop more effective ways of working. For example, in the design, development and delivery of the HORIZONS Programme alongside other stakeholders.

The URG advises on all aspects of the Programme such as the way participants are recruited, updated and contacted within the HORIZONS Programme. The group also advises on study design and participant burden and contributes to and reviews study documentation. We invite our URG members to attend events such as the Programme Launch, and they are supported by the HORIZONS' team to contribute to the Programme through means including Knowledge Café Event co-facilitation, data interpretation, paper writing and conference presentations.

We will hold Knowledge Café events in the community during the life of the Study to bring together the public and people living with and beyond cancer to support involvement, engagement as well as public awareness and understanding of the HORIZONS Programme. These events will be advertised using various media to ensure that we engage with and involve the public across the UK. We will proactively seek engagement with and involvement of those typically under-represented in research, e.g. younger and older people, black and minority ethnic groups and those with lower health literacy. The purpose of these events will be to critically examine and develop the research methods to broaden the reach of involvement and participation in the HORIZONS Programme and contribute to the development of new grant applications.

PPI Research Partners will receive training as appropriate for their role within the HORIZONS Programme. This is likely to include Macmillan's *Building Research Partnerships* course designed for professionals and lay people to support PPI in research. PPI Research Partners will also receive programme specific training from the HORIZONS Programme team to support their involvement in the Programme. This will include training in chairing URG meetings. Research Partners will, following INVOLVE guidelines, be paid for their time and reimbursed their expenses (including travel, subsistence and carer costs) for attending meetings and undertaking other PPI activities.

8.6 Regulatory Compliance

Before any participating centre can enrol patients into the Study, the CI / or designee will ensure that confirmation of capacity and capability and agreement to the statement of activities is received from NHS Research and Development.

Substantial and non-substantial amendments will be submitted to HRA for approval with respect to regulatory compliance and will be managed in line with the HRA advice regarding handling of amendments with participating NHS centres.

8.7 Protocol compliance

Accidental protocol deviations will be documented on the relevant forms and reported to the CI and Sponsor immediately.

Deviations from the protocol which are found to frequently recur are not acceptable, will require immediate action and could potentially be classified as a serious breach.

Steps will be taken to ensure that questionnaires are sent out on time by tracking patients using appropriate software.

8.8 Data protection and patient confidentiality

All investigators and study participating centre staff must comply with the requirements of the current data protection regulations with regards to the collection, storage, processing and disclosure of personal information and will uphold the Act's core principles.

The data will be handled in compliance with GCP guidelines and in accordance with current Data Protection regulations, following procedures as laid out by the Sponsor organisation (UHSFT). All data will remain confidential at all times.

Wherever possible, paper data will be anonymised and stored in locked filing cabinets in secure office premises at the University of Southampton. Only members of the HORIZONS Coordinating Centre will have access to these filing cabinets. Paper forms will be identifiable only by Study ID number. The register of participants' Study IDs and corresponding names and addresses will be stored securely and separately. Clinical and questionnaire data will be stored separately from patient identifiable data and securely stored in locked filing cabinets at the HORIZONS Coordinating Centre. The CI will be the data guardian and will keep a copy of all study documents, patient consent forms and any patient identification lists for ten years from the end of the Study (the HRA define this as the end of collection of all data required to answer the research questions in the protocol). All electronic data will be stored on a secure, password-protected University of Southampton database server, accessible only to the research team. All data will be anonymised prior to leaving the HORIZONS Coordinating Centre premises for data processing and / or statistical analysis. See section 8.12 regarding access to the final study dataset.

8.9 Data Quality

Staff at the HORIZONS Coordinating Centre will be responsible for overseeing the handling and management of all study data. Paper copies of questionnaires and other CRFs will be checked upon receipt at the offices of the HORIZONS Coordinating Centre and any discrepancies or missing data will be queried. Double data entry will be used if possible for entry of the data from paper questionnaires into electronic databases. Electronic data will be checked for accuracy in a random sample of questionnaires, as specified in a statistical monitoring plan.

Missing data

Active steps will be taken to minimise missing data. These will include:

- Obtaining full contact details.
- Reminders to patients via telephone calls, emails or letters.
- Checks with the clinical team to determine if the patient is alive or has changed address.

If questionnaires have not been returned within two weeks, the HORIZONS Coordinating Centre will contact the patient by telephone, email or postal reminder. A second questionnaire or reminder email will then be sent following a further two weeks. If no response to a second questionnaire the patient will not be approached again, until the subsequent annual follow-up questionnaire is due.

Measures to minimise bias

Selection:

- Patients will be identified through a systematic screening process.
- Patients' eligibility to participate will be assessed using a standardised procedure.
- Non-identifiable data regarding reasons for non-entry will be collected on those who choose not to participate.
- Non-identifiable socio-demographic data will be collected (with verbal consent / agreement) on those who choose not to participate in the Study.
- Anonymised data will also be collected for those who were 'missed' i.e. eligible but not invited to participate (e.g. due to logistical reasons).

Outcome measurement and analysis:

- All outcomes are self-rated.
- Strenuous efforts will be made to reduce missing data and maintain subjects in the cohorts, including checks to ensure patients have not moved or died, reminders or repeat questionnaires being mailed on non-response and telephone calls made for missing data.

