On receipt of returned questionnaires these will be checked for completeness. Participants will be contacted by the HORIZONS Coordinating Centre (for example by telephone, email, letter) to ask about whether sections were missed in error and if possible complete missing items in order to reduce the amount of missing data. Mailing of paper questionnaires, or an email reminder to participants electing to complete questionnaires online, will take place within three weeks of the due date of assessment to aim for data collection to be completed as close as possible to the specified assessment date. Participants will be asked to record the date of completion of questionnaires. Prior to contacting participants regarding completion of the next questionnaire the participants' clinical team will be contacted to request confirmation that the participant is alive and the participants' address has not changed. If the clinical team are unable to confirm whether the participant is alive and has not moved by the due date of assessment and all reasonable efforts to acquire this information in a timely fashion have been explored (e.g. GP contact, other hospital sites), the questionnaire will be sent with a notice informing the participant that their status was not confirmed prior to contact. Participants will also be advised to contact the Coordinating Centre if their information has changed or is not correct. The same follow-up protocol for non-response will be followed at each time-point (see consent and non-participation and withdrawal, sections 7.5 and 7.6).

Medical details CRF

The medical details CRF will be completed by the clinical team / researcher at baseline, six and twelve months and then annually for all patients who provided consent. Information including cancer type, stage, treatment, co-morbid conditions, recurrence and survival will be abstracted from clinical records. As part of the extended follow-up, brief medical information will be collected via self-reported medical status questions on follow-up questionnaires.

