7.6. Non-participation and withdrawal

The right of patients to refuse to participate without giving reasons will be respected. Patients will remain free to withdraw from the Study at any time without giving a reason. At all stages the research team will endeavour to record reasons for non-participation. The participating centre will hold a list of eligible patients (screening log) and supply non-identifiable details of the number of eligible patients to the HORIZONS Coordinating Centre. Where possible, this information will include details of reasons for non-participation. Patients who decline any participation in the Study will have their Study ID amended by the addition of the letter D to the original Study ID, and use of XX in place of initials on the screening log (for example, XX01B004D), and the reason for their decision not to participate (if given) will also be added to the screening log.

All eligible patients should be approached. However, if there is a legitimate reason for not approaching a particular patient, then their Study ID also needs to be amended by the addition of the letter M, and use of XX in place of initials to the original Study ID on the screening log (for example, XX01B005M). The reason for the missed approach must also be added to the screening log. The screening log must be completed and posted / emailed/ faxed (as above) to the HORIZONS Coordinating Centre.

If questionnaires have not been returned following consent, the HORIZONS Coordinating Centre /Participating Centre will contact the patient to remind them about questionnaire completion. A duplicate questionnaire or reminder email will then be sent. If no response is received to a duplicate questionnaire the patient will not be approached again, until the next follow-up questionnaire is due.

At the follow-up time points, if the questionnaire has not been returned after three weeks, a reminder letter and/or duplicate questionnaire will be sent. If no response is received to a duplicate questionnaire the patient will not be approached again, until the next follow-up questionnaire is due.

If a participant wishes to withdraw they will be given the information to contact the HORIZONS Coordinating Centre to discuss their concerns about participation. If the participant would like to withdraw they will be sent a withdrawal form (or this can be completed over the telephone with a participant) which will give them three options for levels of withdrawal:

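### The reminder paragraph in Protocol 8.9 contradicts the non-response rule in 7.6 that 5.4 designates; where 8.9 is followed, 12-month non-responders would not be sent the 18-month questionnaire

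*Protocol*

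**What the plan says.** Three sections of the Protocol bear on this.

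- **5.4 Methods of data collection** sets one rule for all waves: "The same follow-up protocol for non-response will be followed at each time-point". The same sentence refers the reader to 7.5 and 7.6. It does not mention 8.9.
- **7.6 Non-participation and withdrawal** gives the rule for follow-up: "At the follow-up time points, if the questionnaire has not been returned after three weeks, a reminder letter and/or duplicate questionnaire will be sent". Contact then resumes at the next wave: "If no response is received to a duplicate questionnaire the patient will not be approached again, until the next follow-up questionnaire is due". A separate paragraph covers the form handed out at consent ("If questionnaires have not been returned following consent, the HORIZONS Coordinating Centre /Participating Centre will contact the patient to remind them about questionnaire completion") and has the same resumption point.
- **8.9 Data Quality**, under its missing-data heading, says: "If questionnaires have not been returned within two weeks, the HORIZONS Coordinating Centre will contact the patient by telephone, email or postal reminder". Then: "A second questionnaire or reminder email will then be sent following a further two weeks". And finally: "If no response to a second questionnaire the patient will not be approached again, until the subsequent annual follow-up questionnaire is due".

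Section 5.3 schedules questionnaires at baseline and at 3, 12, 18 and 24 months, with annual assessments from T5. Section 5.2.1 makes QLACS the primary outcome and includes it at every wave.

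**The concern.** The two rules cannot both be followed. They differ on when the first reminder goes out, on when the second mailing goes out and, most importantly, on when a silent participant is next contacted. The 8.9 version stands in the part of the protocol that lists steps to reduce missing data, which is where a data manager would look.

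Some waves are not annual, so waiting for an annual form can mean that a scheduled form is never sent. The study itself would then turn one missed questionnaire into at least two, and the second gap would be determined by the first. Section 5.5 plans generalised estimating equations and group-based trajectories for change in QLACS, and says that patterns of missing data will be examined. A form that was never sent looks the same in the dataset as one that was sent and not returned, unless dispatch is recorded. The 18-month wave is the one that section 5.3 assigns to further adaptation and the early stages of recovery.

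There is also a compliance side. Section 8.7 treats frequently recurring deviations as unacceptable, yet staff who follow either section routinely depart from the other.

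**Working it through.** The protocol states no figure on this point, so there is none to reproduce. The sample-size section allows for 10% withdrawal and for survival, but gives no response rate by wave. The check is to apply each rule to the schedule.

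**Inputs.** Waves from 5.3: 0, 3, 12, 18 and 24 months, then annual (36, 48, 60 and so on). Resumption point from 7.6: the next scheduled wave. Resumption point from 8.9: the next annual wave. Annual can be read in two ways: the 12- and 24-month waves count because they fall on anniversaries, or only T5 onward counts, because those are the only waves that 5.3 labels annual.

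**Next questionnaire sent after a missed follow-up wave (months):**

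| Missed | 7.6 | 8.9, with 12 and 24 as annual | 8.9, with only T5 onward as annual |
|---|---|---|---|
| 3 | 12, none skipped | 12, none skipped | 36, skips 12, 18 and 24 |
| 12 | 18, none skipped | 24, skips 18 | 36, skips 18 and 24 |
| 18 | 24, none skipped | 24, none skipped | 36, skips 24 |
| 24 | 36, none skipped | 36, none skipped | 36, none skipped |
| 36 | 48, none skipped | 48, none skipped | 48, none skipped |

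The loss of the 18-month wave after a missed 12-month wave occurs on both readings of 8.9. The other skips depend on the narrower reading. From the 24-month wave onward the two sections agree on when contact resumes.

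**Reminder timing.** In 7.6 there is one step, at week 3. In 8.9 the reminder is at week 2 and the second questionnaire at week 2 + 2 = 4. The gap is 3 − 2 = 1 week for the reminder and 4 − 3 = 1 week for the second mailing.

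**Illustration of scale only.** These rates are assumptions, not protocol figures. Suppose 10% to 30% of 1,000 participants sent the 12-month form do not respond, and 8.9 is applied to all of them. Then 1,000 × 0.10 = 100 to 1,000 × 0.30 = 300 are not sent the 18-month form. If 20% to 50% of those would have answered, between 100 × 0.20 = 20 and 300 × 0.50 = 150 QLACS observations are lost. The width of that range shows how little can be said about size from the document.

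**The case against.** The strongest reply is that the protocol already settles precedence. Section 5.4 sends the reader to 7.5 and 7.6 for the non-response rule, 7.6 is the more specific text, and 8.9 reads like a paragraph that was not updated. This stands. A reader might infer that the study deletes the 18-month wave by design; the documents do not support that, because the rule they designate skips nothing. What remains is a contradictory instruction in current text.

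Other stronger readings also go too far:

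- **That a missed baseline form costs the 3-month form.** The general wording of 8.9 could be stretched to baseline, but 7.6 has its own paragraph for that case. Section 5.4 also says that patients who, exceptionally, cannot complete baseline are still sent follow-up questionnaires.
- **That any missed wave costs the next one.** If the 12- and 24-month waves count as annual, then among the follow-up waves only a missed 12-month form has this effect.
- **That the different reminder intervals materially spread completion dates.** The gap is about one week at each step. Section 5.4 already allows mailing within three weeks of the due date and asks participants to record the completion date.
- **That the people lost would be those in poorer health.** Nothing in the protocol shows this for the cohort. Its Rationale says that people with problems are the likelier responders to cross-sectional surveys, so even the direction is open.

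It can also be said that a correction comes late. Appendix 7 describes a cohort already recruited, with most participants around 18 to 24 months after treatment. For them the 3- and 12-month waves are past, and what remains is largely annual, where the sections agree on resumption. This limits what a correction can still save. It does not remove the need to know which rule was used.

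**Conclusion.** The point holds as an internal contradiction with a definite consequence if the wrong section is followed. Sections 7.6 and 8.9 conflict on reminder timing and on resumption of contact, and 5.4 designates 7.6. Under 8.9 a participant who misses 12 months is not sent the 18-month QLACS, nor the 24-month one if annual means T5 onward. Under 7.6 nothing is withheld.

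The size of the loss cannot be derived from the protocol. It depends on how often 8.9 was applied instead of 7.6, on 12-month non-response, and on how many of those non-responders would have replied later; none of these is given. It is confined to participants who still had non-annual waves ahead when the rule was applied. The difference in reminder interval should be tidied up but carries no weight by itself. The correction is worth making because it costs almost nothing and the missing data at stake are primary-outcome data.

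**What to change.** Replace the reminder paragraph in 8.9 with a reference to 7.6, so that the protocol holds one reminder interval and one resumption rule: re-approach at the next scheduled questionnaire, whichever wave that is, unless the participant has withdrawn.

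For waves already completed, record which rule was applied and, for each participant and wave, whether a questionnaire was sent. Forms never sent can then be separated from non-response in the longitudinal analysis. Section 8.7 provides for software tracking of questionnaire mailings, so the dispatch information should largely exist; that is an assumption to confirm.

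The cost is one paragraph in the next amendment and one extract from the tracking records. No contacts are added beyond those 7.6 already requires. The change cannot recover forms that were not sent in the past.

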8.10 Indemnity

UHSFT as Sponsor provides NHS to NHS indemnity. University Staff will be covered by the University of Southampton's Professional Indemnity and Clinical Trials Insurance for the conduct of the research.

8.11 Amendments

If the HORIZONS Coordinating Centre, with the agreement of the Sponsor, wishes to make a substantial amendment to the original application or the supporting documents, the HORIZONS Coordinating Centre will submit a valid notice of amendment to the REC for consideration. The HORIZONS Coordinating Centre will seek confirmation from the Sponsor on whether an amendment is substantial or non-substantial for the purposes of submission to the REC.

Amendments will be submitted in IRAS to the HRA, which will determine whether the amendment requires notification to English participating centres or may be implemented immediately (subject to REC approval were necessary). Amendment processes for participating centres in devolved nations will be followed. The HORIZONS Coordinating Centre will manage amendments in line with the HRA advice regarding participating NHS participating centres.

The amendment history is tracked in this protocol in Appendix 2.

8.12 Access to the final study dataset

The full study dataset will be available to research staff within the HORIZONS Coordinating Centre, including the statistician(s) who will be analysing the data. Participating centres will not have access to the complete dataset while the Study is ongoing and the main results are being analysed and reported. If the participating centres investigators or other researchers wish to access the Study data for the purposes of secondary data analysis then a formal request will need to be made to the HORIZONS Coordinating Centre for consideration. We will design and implement processes to ensure timely open access to the HORIZONS Programme data to a range of communities of research and practice, (e.g. through the ESRC UK data archive <http://www.data-archive.ac.uk/>). Strict regulations are in place to ensure appropriate use of such archived data. Patients will be asked to consent to the use of their anonymised data in future secondary analyses.

9 DISSEMINATION POLICY

9.1 Dissemination policy

An annual dissemination policy will be agreed with Macmillan (the Funder) to ensure timely dissemination of study findings to change practice and improve patient care. We will engage with our SAB, Macmillan and the University of Southampton to ensure maximum publicity and benefit. Findings will be widely disseminated through Macmillan, high impact publications, conference presentations and stakeholder events. We will make recommendations for where to target services and resources for cancer survivors. We will work with service users through our PPI events to disseminate study findings and discuss the progress of the Study.

We intend HORIZONS to be a high profile resource (e.g. website; regular news reports) and work closely with Macmillan, the University of Southampton and other avenues recommended by the SAB to maximise publicity and dissemination of study outputs. HORIZONS has a dedicated website www.HORIZONS-hub.org.uk.

